4.4.14 Therapy Administration

All patients will be treated with the same dose for both ipilimumab and pembrolizumab. Intravenous pembrolizumab 200 mg over 30 (± 5) minutes plus intravenous ipilimumab 1 mg/kg over 90 (± 15) minutes every 3 weeks for four doses, followed by intravenous pembrolizumab 200 mg every 3 weeks for up to 2 years or disease progression, intolerable toxicity, withdrawal of consent, or investigator decision.

4.4.15 Management of Patients with Disease Progression

In the absence of unacceptable toxicity, patients who meet criteria for disease progression will be permitted to continue study treatment if they meet all of the following criteria:

- Evidence of clinical benefit, as determined by the investigator following a review of all available data
- Absence of symptoms and signs (including laboratory values) indicating unequivocal progression of disease
- Absence of decline in ECOG Performance Status that can be attributed to disease progression
- Absence of tumor progression at critical anatomical sites (e.g., leptomeningeal disease) that cannot be managed by protocol-allowed medical interventions

4.5 SUPPORTIVE CARE GUIDELINES

Subjects should receive appropriate supportive care measures as deemed necessary by the treating investigator. Suggested supportive care measures for the management of adverse events with potential immunologic etiology are outlined below. Where appropriate, these guidelines include

Low-Dose Ipilimumab with Pembrolizumab – University of Texas MD Anderson Cancer Center

2018-0875, Version 1.6

Proprietary Information of MD Anderson

the use of oral or intravenous treatment with corticosteroids as well as additional anti-inflammatory agents if symptoms do not improve with administration of corticosteroids. Note that several courses of steroid tapering may be necessary as symptoms may worsen when the steroid dose is decreased. For each disorder, attempts should be made to rule out other causes such as metastatic disease or bacterial or viral infection, which might require additional supportive care. The treatment guidelines are intended to be applied when the investigator determines the events to be related to pembrolizumab.

Note: if after the evaluation the event is determined not to be related, the investigator does not need to follow the treatment guidance (as outlined below). Refer to Section 8.0 for dose modification.

It may be necessary to perform conditional procedures such as bronchoscopy, endoscopy, or skin photography as part of evaluation of the event.

- **Pneumonitis:**

- For **Grade 2 events**, treat with systemic corticosteroids. When symptoms improve to Grade 1 or less, steroid taper should be started and continued over no less than 4 weeks.
- For **Grade 3-4 events**, immediately treat with intravenous steroids. Administer additional anti-inflammatory measures, as needed.
- Add prophylactic antibiotics for opportunistic infections in the case of prolonged steroid administration.

- **Diarrhea/Colitis:**

Subjects should be carefully monitored for signs and symptoms of enterocolitis (such as diarrhea, abdominal pain, blood or mucus in stool, with or without fever) and of bowel perforation (such as peritoneal signs and ileus).

- All subjects who experience diarrhea/colitis should be advised to drink liberal quantities of clear fluids. If sufficient oral fluid intake is not feasible, fluid and electrolytes should be substituted via IV infusion. For Grade 2 or higher diarrhea, consider GI consultation and endoscopy to confirm or rule out colitis.
- For **Grade 2 diarrhea/colitis**, administer oral corticosteroids.
- For **Grade 3 or 4 diarrhea/colitis**, treat with intravenous steroids followed by high dose oral steroids.
- When symptoms improve to Grade 1 or less, steroid taper should be started and continued over no less than 4 weeks.

- **Type 1 diabetes mellitus** (if new onset, including diabetic ketoacidosis [DKA]) or \geq Grade 3 Hyperglycemia, if associated with ketosis (ketonuria) or metabolic acidosis (DKA)

- For **T1DM or Grade 3-4 Hyperglycemia**
 - Insulin replacement therapy is recommended for Type I diabetes mellitus and for Grade 3-4 hyperglycemia associated with metabolic acidosis or ketonuria.
 - Evaluate patients with serum glucose and a metabolic panel, urine ketones, glycosylated hemoglobin, and C-peptide.

- **Hypophysitis:**

- For **Grade 2 events**, treat with corticosteroids. When symptoms improve to Grade 1 or less, steroid taper should be started and continued over no less than 4 weeks. Replacement of appropriate hormones may be required as the steroid dose is tapered.

Proprietary Information of MD Anderson

- For **Grade 3-4** events, treat with an initial dose of IV corticosteroids followed by oral corticosteroids. When symptoms improve to Grade 1 or less, steroid taper should be started and continued over no less than 4 weeks. Replacement of appropriate hormones may be required as the steroid dose is tapered.

- **Hyperthyroidism or Hypothyroidism:**

Thyroid disorders can occur at any time during treatment. Monitor patients for changes in thyroid function (at the start of treatment, periodically during treatment, and as indicated based on clinical evaluation) and for clinical signs and symptoms of thyroid disorders.

- **Grade 2** hyperthyroidism events (and **Grade 2-4** hypothyroidism):
 - In hyperthyroidism, non-selective beta-blockers (e.g. propranolol) are suggested as initial therapy.
 - In hypothyroidism, thyroid hormone replacement therapy, with levothyroxine or liothyroinine, is indicated per standard of care.
- **Grade 3-4** hyperthyroidism
 - Treat with an initial dose of IV corticosteroid followed by oral corticosteroids. When symptoms improve to Grade 1 or less, steroid taper should be started and continued over no less than 4 weeks. Replacement of appropriate hormones may be required as the steroid dose is tapered.

- **Hepatic:**

- For **Grade 2** events, monitor liver function tests more frequently until returned to baseline values (consider weekly).
 - Treat with IV or oral corticosteroids
- For **Grade 3-4** events, treat with intravenous corticosteroids for 24 to 48 hours.
- When symptoms improve to Grade 1 or less, a steroid taper should be started and continued over no less than 4 weeks.

- **Renal Failure or Nephritis:**

- For **Grade 2** events, treat with corticosteroids.
- For **Grade 3-4** events, treat with systemic corticosteroids.
- When symptoms improve to Grade 1 or less, steroid taper should be started and continued over no less than 4 weeks.

- **Management of Infusion Reactions:** Signs and symptoms usually develop during or shortly after drug infusion and generally resolve completely within 24 hours of completion of infusion.

See Table 4 for treatment guidelines for subjects who experience an infusion reaction associated with administration of Pembrolizumab.

Proprietary Information of MD Anderson

4.6 SUBJECT DISCONTINUATION

4.6.1 End of Treatment

Patients complete protocol treatment of the investigational combination after receiving 4 doses of Ipilimumab + Pembrolizumab which occurs after completion of Cycle 4.

Pembrolizumab monotherapy treatment may continue up to a total of 35 doses.

4.6.2 Withdrawal

Subjects who discontinue/withdraw from treatment prior to completion of the treatment regimen should be encouraged to continue to be followed for all remaining study visits. However, patients have the right to voluntarily withdraw from the study at any time for any reason. In addition, the investigator has the right to withdraw a patient from the study at any time. Reasons for withdrawal from the study may include, but are not limited to the following:

- Patient withdrawal of consent at any time
- Any medical condition, determined by the investigator that may jeopardize the patient's safety if he or she continues in the study
- Patient becomes pregnant
- Investigator determines it is in the best interest of the patient
- Patient non-compliance

When a subject discontinues/withdraws from participation in the trial, all applicable activities scheduled for the final trial visit should be performed at the time of discontinuation. Any adverse events which are present at the time of discontinuation/withdrawal should be followed in accordance with the safety requirements outlined in Section 7.1.

Subjects who

- a) attain an investigator-determined CR or

a PR and complete treatment with at least one dose of ipilimumab may discontinue treatment with IPI with the option of restarting the second course phase if they meet the criteria specified in section 7.1.5.2.1. After discontinuing treatment following assessment of CR, these subjects should return to the site for a safety follow-up Visit and then proceed to the follow-up period of the study and survival follow-up.

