Subjects who attain an investigator-determined confirmed CR may consider stopping trial treatment after receiving up to 4 doses of ipilimumab and at least 24 weeks of pembrolizumab. In addition, if a confirmed CR per modified RECIST 1.1 is attained, at least two additional treatments of pembrolizumab must be received prior to treatment discontinuation. Subjects who stop pembrolizumab with SD or better per modified RECIST 1.1 may be eligible for retreatment with a maximum of 17 doses of pembrolizumab and 4 doses of ipilimumab if they progress after stopping pembrolizumab at the discretion of the investigator according to the criteria in section 7.1.5.2.1; this retreatment will be the second course phase. Response or progression in the second course phase will not count towards the CBR or PFS endpoints in this trial. The decision to retreat will be at the discretion of the investigator only if no cancer treatment was administered since the last dose of pembrolizumab, the subject still meets the safety parameters listed in the inclusion/exclusion criteria and the trial remains open (refer to section 7.1.5.2.1 for further details).

After the end of protocol treatment, each subject will be followed for 30 days for AE monitoring. (SAEs will be collected for 90 days after the end of treatment). Subjects who discontinue treatment for reasons other than disease progression will have survival follow-up (SFU) for disease status until disease progression, initiating a non-study cancer treatment, withdrawing consent, or becoming lost to follow-up. All subjects will be followed by telephone contact for OS until death, withdrawal of consent or the end of the trial, whichever comes first

Proprietary Information of MD Anderson

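### For a complete response, Sections 3 and 4.6.2 conflict on when treatment may stop, and 4.6.2 leaves unclear which drug stops

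*Combined protocol and SAP*

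**What the plan says.** Section 3 (Study Design) addresses patients who "attain an investigator-determined confirmed CR". They "may consider stopping trial treatment after receiving up to 4 doses of ipilimumab and at least 24 weeks of pembrolizumab". It adds that, once the CR is confirmed by modified RECIST 1.1, "at least two additional treatments of pembrolizumab must be received prior to treatment discontinuation". It gives no stopping rule for PR. On retreatment it says: "Subjects who stop pembrolizumab with SD or better per modified RECIST 1.1 may be eligible for retreatment", subject to progression after the stop, other conditions, and criteria in a Section 7.1.5.2.1.

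Section 4.6.2 (Withdrawal) addresses patients with a CR as judged by the investigator, with no mention of confirmation, or with a PR. Of these it says: "complete treatment with at least one dose of ipilimumab may discontinue treatment with IPI with the option of restarting the second course phase". The second-course criteria are again placed in Section 7.1.5.2.1. The next sentence reads: "After discontinuing treatment following assessment of CR, these subjects should return to the site for a safety follow-up Visit", after which they enter the follow-up period and survival follow-up.

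Section 7.1.5.2.1 appears neither in the table of contents nor in the text. Section 7.1 has one subsection, 7.1.1.

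**The concern.** Both sections deal with a patient who has responded and may come off treatment, but they set different conditions. Section 3 has three protections against stopping too soon: confirmation, a pembrolizumab minimum, and further treatments after confirmation. Section 4.6.2 has none of them, yet it places CR patients in off-treatment follow-up. The drug it names is ipilimumab, while the consequences it describes fit a patient who has stopped everything. The section that both cite for second-course criteria cannot be consulted.

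Two patients with the same CR could therefore come off treatment months apart, each in line with one of the two sections. At stake are the regimen that complete responders receive, the period over which their adverse events are recorded, and the regularity of the scans that date their progression.

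**Working it through.** The plan gives no figure of its own on this point, so the check compares the texts and then does simple exposure arithmetic.

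**1. The conditions for CR, side by side**

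| Condition | Section 3 | Section 4.6.2 |
|---|---|---|
| CR confirmed? | Yes | Not stated |
| Ipilimumab | Up to 4 doses | At least 1 dose |
| Pembrolizumab minimum | 24 weeks | None stated |
| Treatments after confirmed CR | At least 2 more | None stated |
| What stops | Trial treatment | Ipilimumab is named; CR patients then leave for follow-up |

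**2. Does reading 4.6.2 as ipilimumab only remove the conflict?**

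Taken alone, the clause naming ipilimumab can coexist with Section 3, which speaks of up to 4 doses. Two neighbouring statements do not fit that reading.
- CR patients go to the safety visit and then to follow-up. In the Section 5 schedule these are post-treatment periods, and note b describes them for patients who have discontinued or completed trial treatment. A patient still on three-weekly pembrolizumab would not be there.
- The second course is offered. Section 3 offers it to patients who have stopped pembrolizumab and then progress.

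Section 4.2.2 provides for stopping ipilimumab alone because of toxicity, and Section 4.6.1 completes the combination after 4 doses. Neither mentions stopping ipilimumab for response. The text therefore leaves open which drug or drugs stop. If both stop, it contradicts Section 3.

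**3. Size of the difference in exposure, if 4.6.2 ends all treatment**

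Inputs: 3-week cycles (Section 4.2); CNS scans at week 6 and every 6 weeks after that (Section 3).
- Section 3 minimum: 24 / 3 = 8 cycles. For a CR seen at week 6 and confirmed at the week-12 scan (assumed here), the two further treatments fall at weeks 12 and 15, so the 24-week minimum decides. For a CR confirmed only at the week-24 scan, the minimum is 8 + 2 = 10 doses.
- Section 4.6.2, earliest case: CR at the week-6 scan, doses at weeks 0 and 3, so 6 / 3 = 2 pembrolizumab doses and 1 to 2 of ipilimumab.
- Difference: 8 − 2 = 6 cycles, or 6 × 3 = 18 weeks.
- Later case: Section 1.2 quotes a median time to response of 2.8 months for the nivolumab combination. This is about 2.8 × 4.35 = 12 weeks, so 12 / 3 = 4 doses, half the Section 3 minimum. That median covers any response; the documents give no time to CR.

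**4. Patients concerned**

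Assumption: Cohort A has the brain CR rate that Section 1.2 quotes for nivolumab plus ipilimumab.
- At 21%: 25 × 0.21 = 5.25, about 5 of 25.
- At 15%, the CR rate in the second trial quoted there: 25 × 0.15 = 3.75, about 4 of 25.

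Neither section says whether the CR must be in the brain or overall. If overall, fewer patients would qualify.

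**5. Which results depend on the section followed**

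- Exposure: directly, as in step 3.
- Safety: Section 7.1 records adverse events until 30 days after treatment ends, and Section 7.1.1 SAEs until 90 days (30 if new anticancer therapy starts). Both windows close sooner after a sooner stop.
- PFS: note f of the Section 5 schedule says that scans in follow-up are ordered as standard of care and that out-of-window scans are not deviations. Progression after an early stop may be dated on looser timing.
- CBR: a patient in CR already counts, taking the six-month qualifier to apply to SD.
- Sample size: treatment duration does not enter Section 6.1. With n = 25, 16% against 35% and one-sided 0.10, power is Φ[(0.19 − 1.2816 × √(0.16 × 0.84 / 25)) / √(0.35 × 0.65 / 25)] = Φ(1.007) = 0.843, which agrees with the stated 84%.

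**The case against.** The strongest reply is that the two sections govern different things: 4.6.2 names ipilimumab, Section 3 governs all trial treatment, and the follow-up sentence in 4.6.2 merely lists the visits for CR patients who have stopped under Section 3. This reading is possible, and it is why Section 4.6.2 is described here as unclear on the drug. But nothing in 4.6.2 refers back to the Section 3 conditions, and the second-course offer does not suit a patient who remains on pembrolizumab. A site would have to supply the link itself.

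A second reply is that patients and investigators may end treatment at any time, so no wording fixes duration. That is true, and reconciling the text will not equalise exposure. Stopping for response nevertheless has its own mandatory conditions in Section 3 and carries a second-course option, and general withdrawal rights do not say which conditions apply.

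A third is that the sentence in 4.6.2 is visibly broken, with an item a) and no item b). Drafting and PDF conversion cannot be told apart here, and the point does not rest on the break.

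It is also fair that 2 doses is an extreme case requiring a CR at the first scan. Appendix 1 requires a RANO CR to last at least 4 weeks; if that is applied, the next scheduled scan is week 12 and the figure is 4 doses.

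**Conclusion.** For CR the conflict stands. Section 3 requires confirmation, 24 weeks of pembrolizumab and two further treatments; Section 4.6.2 states none of these and moves CR patients to off-treatment follow-up. If 4.6.2 ends all treatment, the earliest exit is after about 2 pembrolizumab doses against at least 8. On the assumed 21% CR rate, about 5 of 25 Cohort A patients are concerned (about 4 at 15%). The effect is on responders' exposure, safety follow-up and PFS scan timing.

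Three stronger conclusions that a reader might draw are not supported.
- That any PR patient may stop all treatment after one ipilimumab dose, which would bring 25 × (0.21 + 0.33) = 13.5, or 13 to 14 of 25, into question. The follow-up sentence names CR only; for PR, a pembrolizumab stop is inferred from the second-course option and is not stated.
- That excluding second-course events from CBR and PFS changes which events count after an early stop. Section 3 offers retreatment only after progression following the stop, and Section 6.2.2 counts that first progression in PFS. The exclusion does not remove it.
- That the primary endpoint or the power is compromised. Neither depends on which section is followed.

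**What to change.** Reconcile Sections 3 and 4.6.2. One passage should state which response qualifies, whether it must be confirmed, the minimum exposure, and whether the option covers ipilimumab, pembrolizumab or both. It should say explicitly whether PR is included and whether the response is judged in the brain or overall. The other section should refer to it. Replace the reference to Section 7.1.5.2.1 in both places with a section that exists, or add the missing criteria. Which clinical rule applies is for the sponsor to decide.

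In the analysis, report by cohort the number of patients who stop for response, with their best response and the ipilimumab and pembrolizumab doses received. The cost is protocol wording and one descriptive table; sample size and the primary analysis do not change.

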4.6.3 End of Study

The end of this study is defined as the date when the last patient, last visit (LPLV) occurs or the date at which the last data point required for statistical analysis or safety follow-up is received from the last patient, whichever occurs later. LPLV is expected to occur 24 months after the last patient is enrolled in the trial.

Proprietary Information of MD Anderson

4.6.4 Post Study Drug Study Follow-up

In this study, clinical benefit rate is the primary endpoint of the study. Post study follow-up is of critical importance and is essential to preserving subject safety and the integrity of the study. Subjects who discontinue study drug must continue to be followed for collection of outcome and/or survival follow-up data as required until death or the conclusion of the study.

4.6.5 Lost to Follow-up

All reasonable efforts must be made to locate subjects to determine and report their ongoing status. This includes follow-up with persons authorized by the subject as noted above. Lost to follow-up is defined by the inability to reach the subject after a minimum of three documented phone calls, faxes, or emails as well as lack of response by subject to one registered mail letter. All attempts should be documented in the subject's medical records. If it is determined that the subject has died, the site will use permissible local methods to obtain the date and cause of death.

The site staff and representative will consult publicly available sources, such as public health registries and databases, in order to obtain updated contact information. If after all attempts, the subject remains lost to follow-up, then the last known alive date as determined by the investigator should be reported and documented in the subject's medical records.

5

SCHEDULE OF ASSESSMENTS

Trial Period:	Screening Phase	Treatment Cycles ^a								End of Treatment	Post-Treatment			
		1	2	3	4	To be repeated beyond 8 cycles					Safety Follow-	Follow Up Visits ^b	Survival Follow-Up	
Treatment Cycle/Title:	Screening	1	2	3	4	5	6	7	8	Discontinuation	At time of Discontinuation	30 days post discontinuation ± 7	Every 6 weeks post discontinuation ± 7	Every 12 weeks ± 7
Scheduling Window (Days):	-28 to 1		± 3	± 3	± 3	± 3	± 3	± 3	± 3					
Administrative Procedures														
Informed Consent	X													
Inclusion/Exclusion Criteria	X													
Demographics and Medical History	X													
Prior and Concomitant Medication Review	X		X	X	X	X	X	X	X	X				
Trial Treatment Administration ^c			X	X	X	X	X	X	X					
Post-study anticancer therapy status												X	X	
Survival Status													X	
Clinical Procedures/Assessments														
Review Adverse Events			X	X	X	X	X	X	X	X	X	X	X	
Physical Examination	X		X	X	X	X	X	X	X	X			X	
Vital Signs, Weight, and Height ^l	X		X	X	X	X	X	X	X	X			X	
Electrocardiogram (12-Lead ECGs)	X													
ECOG Performance Status	X		X	X	X	X	X	X	X	X			X	
Laboratory Procedures/Assessments: analysis performed by LOCAL laboratory														
Pregnancy Test – Urine or Serum β-HCG ^d	X		X		X		X		X		X		X ^k	

Trial Period:	Screening Phase	Treatment Cycles ^a								End of Treatment	Post-Treatment		
		1	2	3	4	To be repeated beyond 8 cycles					Discontinuation	Safety Follow-	Follow Up Visits ^b
Treatment Cycle/Title:	Screening												
Scheduling Window (Days):	-28 to 1			± 3	± 3	± 3	± 3	± 3	± 3	At time of Discontinuation	30 days post discontinuation ± 7	Every 6 weeks post discontinuation ± 7	Every 12 weeks ± 7
Coagulation ^e	X												
CBC with Differential	X		X	X	X	X	X	X	X	X		X	
Comprehensive Serum Chemistry Panel	X		X	X	X	X	X	X	X	X		X	
Urinalysis	X		X	X	X	X	X	X	X	X			
T3, FT4 and TSH	X		X		X		X		X	X			
Efficacy Measurement													
Tumor Imaging ^f	X				X		X		X	X			
Tumor Biopsies/Archival Tissue Collection/Correlative Studies Blood													
Tissue Collection													
Archival Tissue ^g	X												
Serial Biopsy ^h	X		X	X			X						
Cerebrospinal Fluid ⁱ	X				X								
Blood Collection													
Correlative Studies ^j			X		X		X		X				

Trial Period:	Screening Phase	Treatment Cycles ^a								End of Treatment	Post-Treatment		
						To be repeated beyond 8 cycles					Safety Follow-	Follow Up Visits ^b	Survival Follow-Up
Treatment Cycle/Title:	Screening	1	2	3	4	5	6	7	8				
		-28 to 1		± 3	± 3	± 3	± 3	± 3	± 3	At time of Discontinuation	30 days post discontinuation ± 7	Every 6 weeks post discontinuation ± 7	Every 12 weeks ± 7
Scheduling Window (Days):													
^a Cycles are 3 weeks (21 days) in duration													
^b Patients who discontinue trial treatment for reasons other than disease progression will move into Follow Up Visits where they will be seen every 6 weeks for one year and then into Survival Follow Up where they will be seen every 12 weeks for another year. Patients who successfully complete 2 years of Pembrolizumab will move directly into Survival Follow Up and be seen every 12 weeks for up to one year. Once a patient is in follow up or survival follow up, restaging scans done out of window will not be deviations as they will be ordered SOC.													
^c Ipilimumab 1mg/kg every 3 weeks up to 4 doses Pembrolizumab will be administered at 200mg every 3 weeks.													
^d See Section 7.4 if a woman of child-bearing potential becomes pregnant while on study.													
^e Prothrombin time/International Normalized Ratio, Activated Partial thromboplastin time.													
^f MRI scan will be performed every 6 weeks for the first year, then ~ every 12 weeks until progression or discontinuation of study treatment, whichever comes later. Imaging window is +/- 7 days. If scans were performed within 4 weeks of discontinuation, repeat scans are not required. When a patient moves into Follow-Up, they will have scans ordered as Standard of Care by their treating physician. Once a patient is in follow up or survival follow up, restaging scans done out of window will not be deviations as they will be ordered SOC. ^g See Section 4.4.7 for additional details.													
^h Patients with biopsable extracranial disease may have tissue collected. See Section 4.4.8. Screening biopsy only required if there is no archival tissue available													
ⁱ Cerebrospinal Fluid will be obtained from up to 5 patients for optional testing. See Section 4.4.12.1.3 for additional details.													
^j See Section 4.4.12.1.2.													
^k Pregnancy testing to be completed at 120 days posttreatment													
^l Height only to be collected at Screening.													

6

STATISTICAL CONSIDERATIONS

